4.6.3. Exploratory

Exploratory analyses of primary and secondary endpoints will be performed for the subgroups defined in section 4.2.6, on the Full Analysis Set, provided that enough subjects are included in each subgroup category for the model to converge.

Primary Endpoint Exploratory Analyses

Descriptive statistics per subgroup and treatment group will be presented and will include the total number of events (HF hospitalisation and CV death), the number (%) of subjects with at least one event, the number (%) of subjects with more than one event, the time on study, and the HF hospitalisation and CV death rates per 100 subject-years.

The negative binomial model described in section 4.6.1 will be repeated including each of the subgroup variable as covariate and an interaction effect between the subgroup variable and the treatment group (one model for each subgroup). The estimated rate of events per 100 subject-years will be presented by subgroup and treatment group with the 95% CI. The estimated rate ratio (95% CI and p-value) between treatment groups for each subgroup will be presented as well as the overall p-value for the interaction. The model will be performed both with and without adjustment for randomisation factors.

For the following subgroups (randomisation factors), the subgroup covariate will be included only once in the model:

- Sex
- Ischaemic Aetiology of HF (ischaemic, non-ischaemic)
- Diagnosis of Heart Failure (newly diagnosed at index hospitalisation versus known documented HF prior index hospitalisation).

For analysis of subgroup by age, the age covariate will be removed from the model and the factor age (by tertiles) will be included instead.

A forest plot of rate ratios from the main analysis and from all different subgroups will be provided.

SAS Code for negative binomial model with subgroup interaction (code may be updated to fit the data):

```
proc genmod data=dataset;
  class armcd (ref='placebo') sex hf_aetio hf_duration country subgrp (ref='2');
  model count = armcd sex age hf_aetio hf_duration country subgrp armcd*subgrp /
  offset=logfu_dur link=log dist=negbin type3;
  lsmeans armcd armcd*subgrp / exp cl diff e;
  ods output lsmeans=lsmeans;
  ods output estimates=estimates;
  ods output modelanova=type3;

  * Trt comparison ;
  estimate 'Treated vs. placebo gr1' armcd 1 -1 armcd*subgrp 1 0 -1 0 /exp
alpha=0.05;
  estimate 'Treated vs. placebo gr2' armcd 1 -1 armcd*subgrp 0 1 0 -1 /exp
alpha=0.05;

  /* Subgroup with 3 categories;
  * Trt comparison;
  estimate 'Treated vs. placebo gr1' armcd 1 -1 armcd*subgrp 0 0 1 0 0 -1 /exp
alpha=0.05;
  estimate 'Treated vs. placebo gr2' armcd 1 -1 armcd*subgrp 1 0 0 -1 0 0 /exp
alpha=0.05;
  estimate 'Treated vs. placebo gr3' armcd 1 -1 armcd*subgrp 0 1 0 0 -1 0 /exp
alpha=0.05;
  run;
logfu_duration is the log-transformed time on study of each subject in years.
```

Secondary Endpoints Exploratory Analysis: Recurrent event analysis

The recurrent event analysis similar to primary endpoint analysis will be repeated by subgroup on all subgroups defined in section 4.2.6 for the following endpoints:

- The composite of recurrent CV hospitalisations or CV death up to 52 weeks after randomisation.
- HF hospitalisations up to 52 weeks after randomisation (analysed as a recurrent event)

Secondary Endpoints Exploratory Analysis: Time to first event analysis

The time to first event analysis described in section 4.6.2 will be repeated for each subgroup defined in section 4.2.6 on the following secondary endpoints:

1. CV mortality analysed as time to first event up to 52 weeks after randomisation.
2. The composite of HF hospitalisations or CV death analysed as time to first event up to 52 weeks after randomisation.

The Cox regression will include the subgroup variable and the interaction between treatment and subgroup effect as a covariate. Hazard ratios, 95% CI and the associated p-value by subgroup will be presented, as well as the p-value of global effect of interaction between treatment and subgroup.

For analyses by subgroup of randomisation factors, the subgroup covariate will be included only once in the model as described earlier. A forest plot of hazard ratios from the main analysis and from all different subgroups will be provided.

SAS Code to be used for time to event Cox proportional hazards regression with subgroup interaction (code may be updated to fit the data):

```
PROC PHREG DATA=test2 ;
  CLASS armcd(ref='Placebo') sex subgrp (ref='2') /param=glm;
  MODEL tfe*event(0)= armcd sex subgrp armcd*subgrp / risklimits type3 rl;
  *hazardratio armcd / at (subgrp=all) cl=wald ;
  contrast "IV FCM. vs Placebo gr1"  armcd 1 -1 subgrp 0 armcd*subgrp 1 0 -1 0
/estimate=exp;
  contrast "IV FCM. vs Placebo gr2"  armcd 1 -1 subgrp 0 armcd*subgrp 0 1 0 -1
/estimate=exp;

  /* Subgroup with 3 categories;
  contrast "IV FCM. vs Placebo gr1"  armcd 1 -1 subgrp 0 armcd*subgrp 0 0 1 0 0 -1
/estimate=exp;
  contrast "IV FCM. vs Placebo gr2"  armcd 1 -1 subgrp 0 armcd*subgrp 1 0 0 -1 0 0
/estimate=exp;
  contrast "IV FCM. vs Placebo gr3"  armcd 1 -1 subgrp 0 armcd*subgrp 0 1 0 0 -1 0
/estimate=exp; */

  ods output ContrastEstimate=ContrastEstimate;
  *ods output HazardRatios=hr ;
  *ods output parameterestimates=parmest;
  ods output modelanova=modelanova;
RUN;
```

Secondary Endpoint exploratory analysis: Number of days lost due to HF hospitalisations or CV death

The number of days lost due to HF hospitalisations or CV death up to 52 weeks after randomisation analysis will be repeated by subgroup for each subgroup defined in section 4.2.6.

A forest plot of ratio ratios from the main analysis and from all different subgroups will be provided.

NYHA functional class exploratory analysis:

NYHA functional class analysis described in section 4.6.2 will be performed by subgroup (see section 4.2.6). The ordered polytomous response model will include the subgroup variable and interaction between treatment and subgroup as covariate. Odd-ratio by subgroup will be provided. For analyses by subgroup of randomisation factors, the subgroup covariate will be included only once in the model. For analysis of subgroup by age, age covariate will be removed from the model and the factor age by tertiles will be included instead. For subgroup of NYHA class, the analysis will be performed on the subset of subjects with NYHA class II or III at baseline and the baseline NYHA class will be included only once in the model.

A forest plot of odds ratios from the main analysis and from all different subgroups will be provided.

SAS Code to be used for subgroup analysis (code may be updated to fit the data):

```
proc genmod data=dataset rorder=internal ;
  class armcd (ref='Placebo') visit usubjid base sex hf_aetio hf_duration country
  subgrp (ref='1') ;
  model score_NYHA = armcd visit base sex age hf_aetio hf_duration country subgrp
  armcd*subgrp / dist=multinomial link=cumlogit TYPE3 ;
  repeated subject=usubjid/ type=IND;
  estimate 'Log OR Treated vs. placebo gr1' armcd 1 -1 armcd*subgrp 0 1 0 -1 /
exp;
  estimate 'Log OR Treated vs. placebo gr2' armcd 1 -1 armcd*subgrp 1 0 -1 0 /
exp;

  /* Subgroup 3 categories
  estimate 'Log OR Treated vs. placebo gr1' armcd 1 -1 armcd*subgrp 0 0 1 0 0 -1
/exp;
  estimate 'Log OR Treated vs. placebo gr2' armcd 1 -1 armcd*subgrp 1 0 0 -1 0 0
/exp;
  estimate 'Log OR Treated vs. placebo gr3' armcd 1 -1 armcd*subgrp 0 1 0 0 -1 0
/exp; */
  ods output estimates=estimates ;
  ods output type3=type3 ;
run;
```

Additional exploratory analyses not described above may be performed if indicated by the medical review(s) of the data.

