4. STATISTICAL METHODS

4.1. Sample Size Justification

The recurrent HF hospitalisation and CV death rates in the control group were extrapolated as 0.9 events/year using the data from the EVEREST study [3] and as 0.61 events/year using the data from the ESC-HF study [4]. For this study, it is anticipated that approximately 35% of subjects will sustain either a CV death or at least one HF hospitalisation. It is also anticipated that 12% of subjects will sustain a CV death. Assuming that 50% of subjects who sustain a CV death will not undergo any prior HF hospitalisation and estimating the average number of HF hospitalisations per subject with at least one HF hospitalisation as 2, the number of events per 100 years of follow-up has been estimated as follows: 12 CV deaths + 2*(35-6) HF hospitalisations, which equates to approximately 70 events/100 years of follow-up for HF hospitalisations and CV death.

Concerning the event rate ratio, it is assumed that there will be a 30% reduction in HF hospitalisations for subjects allocated to FCM and that CV death rates will be similar between the FCM and placebo groups. It is therefore assumed that the rate ratio between FCM and placebo for the composite of recurrent HF hospitalisations and CV deaths will be approximately 25%.

The dispersion factor used in negative binomial regression is a measure of the mean-variance. There are currently insufficient data to estimate the negative binomial dispersion. For this sample size calculation, a dispersion factor (K) of 1 was assumed.

The sample size calculation was done in the software NCSS PASS-14 [5], using the sample size formula proposed by Zhu and Lakkis 2014 [6] to compare two negative binomial rates.

Assuming a rate of recurrent HF hospitalisation or CV death of 0.7 events/year in the placebo group, a total of 1,000 subjects (500 per study drug group) would be required to demonstrate a statistically significant rate ratio of 0.75 (i.e., 25% reduction of recurrent hospitalisations or deaths between the FCM and placebo groups) with a power of 80% and a 2-sided alpha of 0.05. Taking into account an expected 9% loss to follow-up, a sample size of 1,100 subjects (550 per treatment group) is planned.

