4.2. General Statistical Methods and Data Handling

4.2.1. General Methods

Tabulations will be produced for appropriate demographic, baseline, efficacy, and safety parameters. For categorical variables, summary tabulations of the number and percentage of subjects within each category of the parameter will be presented (with a category for missing data if appropriate). For continuous variables, the mean, median, standard deviation (SD), first and third quartiles (Q1 and Q3), and minimum and maximum values will be presented. The level of significance to be used for tests will be 0.05, two-sided.

Listings will be sorted by subject ID unless specified otherwise.

Label of the group treated with Intra Venous Ferric CarboxyMaltose will be “FCM”, placebo group will be labelled as “Placebo”.

All outputs will be incorporated into Word files, sorted and labelled according to the International Council for Harmonisation (ICH) recommendations, and formatted to the appropriate page size(s).

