4.2.6. Subpopulations

Some analyses will be performed on the following subgroups:

- Hb level at baseline (< 12, ≥ 12 g/dL).
- Ferritin level at baseline by tertiles.
- Ferritin level at baseline (< 100 ng/mL, ≥ 100 ng/mL).
- TSAT category at baseline by tertiles.
- TSAT category at baseline (< 20%, ≥ 20%).
- Sex.
- Age by tertiles.
- Renal function at baseline defined as No CKD, CKD stages I and II, and CKD stages III, IV, or V at baseline medical history.
- Estimated glomerular filtration rate (eGFR) value at baseline by tertiles. The eGFR value at baseline will be calculated using the CKD-EPI formula and the baseline creatinine value.
- Ischaemic Aetiology of HF (ischaemic, non-ischaemic).
- NYHA at baseline (NYHA II, NYHA III, if applicable, i.e. if there are at least 10% of subjects by NYHA class and treatment group. NYHA I and IV not included).
- NT-pro BNP (pg/mL) or BNP (pg/mL) at baseline assigned to First tertile, Second tertile or Third tertile. Tertiles of NT-proBNP and BNP at baseline in FAS regardless of treatment group will be computed (for each parameter separately) and subjects will be assigned to these groups. In case subject has both values collected at baseline, NT-proBNP will be used and subject will be assigned according to computed NT-proBNP tertiles.
- Left ventricular ejection fraction (%) at baseline Left ventricular ejection fraction (LVEF) < 25%, ≥ 25% until < 40%, and ≥ 40% until < 50%
- Diagnosis of Heart Failure (newly diagnosed at index hospitalisation, known documented HF prior index hospitalisation).
- Subjects hospitalised for an episode of Acute Heart Failure in the previous 12 months prior Index Hospitalisation (yes, no).
- Creatinine at baseline by tertiles.

For subgroups defined by tertiles, tertiles will be computed on the FAS regardless of treatment group.

Additionally, following subgroups will be investigated for exploratory purposes:

- Geographical region (Latin America [Argentina, Brazil], Asia [Israel, Lebanon, Singapore], South and Eastern Europe [Italy, Croatia, Georgia, Romania, Ukraine], Central and Western Europe [Netherlands, Poland, United Kingdom, Spain, Sweden])
- Subjects with ARNI (yes, no)
- Subjects with ACE or ARB or ARNI, at least one of these groups (yes, no)
- Subjects with beta-blockers (yes, no)
- Subjects with Aldosterone Antagonists (yes, no)

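### Exploratory tests of effect modification by continuous baseline measures use only cut categories; an added continuous interaction test would recover power against a graded effect

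*SAP*

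**What the plan says.** SAP 4.2.6 defines the subgroups:

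- Haemoglobin has one cut: "Hb level at baseline (< 12, ≥ 12 g/dL".
- Ferritin is grouped twice, by tertiles and at 100 ng/mL. TSAT is also grouped twice, by tertiles and at 20%.
- Age, eGFR and creatinine are grouped by tertiles.
- LVEF has three bands with boundaries at 25% and 40%.
- NT-proBNP or BNP is grouped by tertiles computed separately for each assay.

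For the tertile groupings, "For subgroups defined by tertiles, tertiles will be computed on the FAS regardless of treatment group".

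SAP 4.6.3 refits the primary negative binomial model once per subgroup variable, "including each of the subgroup variable as covariate and an interaction effect between the subgroup variable and the treatment group". The sample code puts the subgroup in the CLASS statement, so the interaction has 1 df for two groups and 2 df for three. The Cox analyses report subgroup hazard ratios "as well as the p-value of global effect of interaction between treatment and subgroup". The NYHA model has the same structure, and the days-lost analysis is repeated on the same subgroups. In the age-subgroup model the continuous age covariate is taken out and tertiles are put in.

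No interaction with a continuous value, scored trend or spline appears. SAP 4.6.3 closes by allowing further exploratory analyses if medical review of the data suggests them. Protocol 12.10.1 names candidate subgroup variables without cut-points.

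**The concern.** Whether the effect of FCM changes with iron status, anaemia, renal function or age is a question that readers will take to the forest plots. The seven measures are recorded on a continuous scale. If the effect rises or falls steadily along one of them, grouping treats everyone within a group as alike, and a nominal three-level factor also spends a second degree of freedom. Both weaken the test, so a real gradient is more likely to be reported as no interaction. The trial is sized for the main effect only, so power for interactions is limited from the start.

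**Working it through.** **Inputs.** SAP 4.2.1: "The level of significance to be used for tests will be 0.05, two-sided". SAP 4.1: "Assuming a rate of recurrent HF hospitalisation or CV death of 0.7 events/year in the placebo group", a "statistically significant rate ratio of 0.75", "with a power of 80% and a 2-sided alpha of 0.05", dispersion K = 1, and 1,100 subjects (550 per arm) after 9% loss. Protocol synopsis, Sample Size: mean follow-up 11 months. The documents give no interaction size and no distribution for any modifier. Both are assumed below and varied.

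**1. The plan's own figure.** Zhu-Lakkis formula with the control-rate null variance and t = 11/12 year:

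- 1/(t × 0.7) = 1.558; 1/(t × 0.525) = 2.078
- V0 = 2 × 1.558 + 2 = 5.117; V1 = 1.558 + 2.078 + 2 = 5.636
- n = (1.960 × √5.117 + 0.842 × √5.636)² / (ln 0.75)² = 499.8, so 500 per arm and 1,000 in total, as stated
- 1,000 / 0.91 = 1,099, against 1,100 planned

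**2. Information kept by a cut.** For an effect linear in the modifier, this is the between-group variance of the group means divided by the total variance.

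| Grouping | Normal modifier | Uniform modifier |
|---|---|---|
| Median split | 2/π = 0.637 | 1 − 1/4 = 0.75 |
| Tertiles | 0.793 | 1 − 1/9 = 0.889 |

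The loss is 21-36% if normal and 11-25% if uniform. With a normal modifier, a two-group cut away from the median loses 38% at 60/40, 42% at 70/30 and 51% at 80/20. LVEF bands with assumed shares of 15-30% / 55% / 15-30% lose about 20-21%. The documents do not give the shares either side of Hb 12, ferritin 100 or TSAT 20%. Ferritin and TSAT also have tertile versions, which limit the loss. Hb does not.

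**3. Power on the trial's inputs.** With 550 per arm, the SE of the log rate ratio is √(5.636/550) = 0.1012. For a modifier in SD units the interaction slope has about the same SE. The non-centrality is (slope/0.1012)² times the fraction kept, on 1 df (continuous or two groups) or 2 df (tertiles). Normal modifier, overall rate ratio 0.75:

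| Slope per SD | Rate ratio at −1 / +1 SD | Continuous | Median split | Tertiles | Points lost (median split / tertiles) |
|---|---|---|---|---|---|
| 0.10 | 0.68 / 0.83 | 16.7% | 12.4% | 11.3% | 4.3 / 5.4 |
| 0.15 | 0.65 / 0.87 | 31.7% | 21.9% | 20.1% | 9.8 / 11.6 |
| 0.20 | 0.61 / 0.92 | 50.6% | 35.1% | 33.1% | 15.5 / 17.5 |
| 0.25 | 0.58 / 0.96 | 69.5% | 50.4% | 49.0% | 19.1 / 20.5 |
| 0.29 | 0.56 / 1.00 | 81.1% | 62.1% | 61.4% | 19.0 / 19.7 |
| 0.35 | 0.53 / 1.06 | 93.3% | 78.8% | 79.3% | 14.5 / 14.0 |

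**4. Simulation.** 600 trials of 1,100 subjects per slope, gamma frailty with K = 1, likelihood-ratio tests. Power (continuous / median split / tertiles) was 33/22/24% at 0.15, 67/49/48% at 0.25 and 80/63/61% at 0.29. With no interaction, rejection was 5.7/5.0/5.8%, so type I error is near nominal for all three.

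**5. Other shapes.** Each case starts from a test with 80% power.

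- Uniform modifier, continuous test at 80%: 68% for a median split and 65% for tertiles, a loss of 12-15 points.
- Normal modifier, continuous test at 80%, tertiles scored as a 1-df trend: 70%, against 60% as a 2-df factor. About half of the tertile loss therefore comes from the extra degree of freedom.
- True step at a median cut, two-group test at 80%: the linear test has about 61%.

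**The case against.** The strongest reply is that this is a modelling preference. The analyses are labelled exploratory, the plan claims no interaction power or hypothesis, and the categorical tests are valid. All of that stands. It bears on priority; it does not show that the cut scale is the better test for a graded effect.

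Several stronger readings are tempting, and the documents do not support them.

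- **That 15-20 points are lost under any graded effect.** At a slope of 0.29 the whole planned benefit disappears between −1 and +1 SD, which is a steep gradient. Weaker gradients lose 4-12 points because every test then has little power.
- **That the modifiers are normal.** Eligibility restricts Hb to 8-15 g/dL (10-15 in three countries), ferritin to at most 299 ng/mL and LVEF to below 50%. Flatter distributions lose less.
- **That a graded dependence is the likely form.** Nothing in either document says so.
- **That the categorical p-values should be replaced.** Protocol 1.1 defines absolute and functional iron deficiency using ferritin 100 and TSAT 20%, and the same values drive eligibility and maintenance dosing. Comparing across them is a legitimate question, and a single linear term can miss a step or a U-shape. Grouping ferritin and TSAT in two ways can be read as covering both forms.
- **That the age model contradicts SAP Section 5.** Section 5 concerns age as an adjustment covariate. Substituting tertiles in the age-subgroup model simply avoids entering age twice.
- **That natriuretic peptide has the same fault.** Assay-specific tertiles put BNP and NT-proBNP on one scale.

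The closing allowance in SAP 4.6.3 does not exclude a continuous test, but it does not pre-specify one.

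**Conclusion.** The point holds as a low-priority improvement. For Hb, ferritin, TSAT, age, eGFR, creatinine and LVEF, the SAP tests effect modification only through two- or three-level factors, and this is the weaker test if the effect is roughly linear in the measure. The information loss is about 20-40% for a normal modifier with a reasonably central cut and about 11-25% for a uniform one. It could exceed 40% where a fixed cut falls well off centre.

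The power cost is about 15-20 points only for strong gradients (0.20-0.33 per SD, normal modifier, where the continuous test has roughly 50-90% power). It is about 10-12 points at 0.15, 4-5 at 0.10 and none for a step at the cut. The slopes and distributions are assumptions; the remaining inputs are the plan's. Only exploratory analyses are affected. The primary result, type I error and sample size do not change.

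**What to change.** In SAP 4.6.3, before unblinding, add for each of the seven measures a pre-specified interaction of armcd with the continuous baseline value (log scale for ferritin and creatinine). Include a simple non-linearity check such as a restricted cubic spline. Apply it in the negative binomial, Cox, days-lost and NYHA models, and name it as the test for a graded effect. Keep the planned categorical estimates, interaction p-values and forest plots, including the cuts at ferritin 100 and TSAT 20%. Leave natriuretic peptide on its assay-specific tertiles.

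The cost is SAP wording and extra model runs on data already collected. There will be more exploratory p-values: seven per outcome, or 7 × 7 = 49 over the seven outcomes with subgroup tables in SAP 7.1, beside the 16 × 7 = 112 subgroup analyses already listed there. They should be labelled exploratory and unadjusted. The linear term assumes a straight line on the chosen scale; the spline check and the retained categories would show a clear departure from it.

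### The three-category contrasts in the negative binomial and Cox subgroup templates do not match the declared reference level, and the Cox template drops four of five covariates

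*SAP*

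**What the plan says.** SAP section 4.6.3 prints three subgroup-by-treatment templates: negative binomial, Cox and NYHA (ordinal). Each has active lines for a two-category subgroup and commented lines, introduced in the first two by "Subgroup with 3 categories", for a three-category one.

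- Negative binomial: the class statement ends with reference level 2 for the subgroup, "class armcd (ref='placebo') sex hf_aetio hf_duration country subgrp (ref='2". Its two-category gr1 line is "estimate 'Treated vs. placebo gr1' armcd 1 -1 armcd*subgrp 1 0 -1 0 /exp".
- Cox: "CLASS armcd(ref='Placebo') sex subgrp (ref='2') /param=glm", with two-category interaction coefficients identical to those of the negative binomial template.
- NYHA: the subgroup reference is level 1, and the two-category gr1 line becomes "estimate 'Log OR Treated vs. placebo gr1' armcd 1 -1 armcd*subgrp 0 1 0 -1".

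The three-category vectors are the same in all three templates: gr1 is "estimate 'Treated vs. placebo gr1' armcd 1 -1 armcd*subgrp 0 0 1 0 0 -1 /exp" in the negative binomial version, gr2 uses `1 0 0 -1 0 0` and gr3 uses `0 1 0 0 -1 0`.

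The Cox subgroup model is "MODEL tfe*event(0)= armcd sex subgrp armcd*subgrp / risklimits type3 rl". The text above it says that the time-to-first-event analysis of section 4.6.2 is repeated by subgroup. The section 4.6.2 model contains sex, age, HF aetiology, HF duration and country, the same five covariates as section 4.2.4. All three templates carry the rider that the code may be updated to fit the data.

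**The concern.** The two-category coefficients change when the reference level changes, as they must. The three-category coefficients do not, so one set of vectors is being used with two different level orders and cannot be right for both.

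If the negative binomial and Cox versions are activated as they stand, the ratio, confidence interval and p-value for level 1 appear under level 2, and the reverse. Level 3 stays correct, so a monotone pattern would look non-monotone: true ratios of 0.60, 0.80 and 1.00 would print as 0.80, 0.60 and 1.00. Readers use such plots to judge whether the effect varies with ferritin, TSAT, renal function or ejection fraction.

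The Cox covariate list is a separate matter and lies in active code. If the template overrode the text, the hazard-ratio forest plots would set an overall ratio adjusted for five covariates beside subgroup ratios adjusted for sex alone.

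**Working it through.** **Layout.** With k subgroup levels, the interaction coefficients are k for FCM followed by k for placebo, each in the stored order of the levels. With `armcd 1 -1`, a 1 in position i and a -1 in position k+i gives the FCM-to-placebo log ratio at the i-th stored level.

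**Ordering rule, from the SAP's two-category lines.**

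- Reference '2', order (1, 2): gr1 `1 0 -1 0` has i = 1, which is level 1; gr2 `0 1 0 -1` has i = 2, which is level 2.
- Reference '1' (NYHA), order (2, 1): gr1 `0 1 0 -1` has i = 2, which is level 1; gr2 `1 0 -1 0` has i = 1, which is level 2.

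Both sets return the labelled group only if the reference level is stored last. That rule therefore reproduces the SAP's own working code.

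**Three-category lines under the same rule.**

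| Line | Vector | i | Reference '1', order 2, 3, 1 (NYHA) | Reference '2', order 1, 3, 2 (negative binomial, Cox) |
|---|---|---|---|---|
| gr1 | 0 0 1 0 0 -1 | 3 | level 1 | level 2 |
| gr2 | 1 0 0 -1 0 0 | 1 | level 2 | level 1 |
| gr3 | 0 1 0 0 -1 0 | 2 | level 3 | level 3 |

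The NYHA lines are right. In the other two templates gr1 and gr2 are exchanged. If the reference option did not reorder the levels (order 1, 2, 3), the vectors would pick levels 3, 1 and 2, so the labels would still be wrong.

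**Numerical check.** Simulated negative binomial counts: 60,000 subjects, placebo rate 0.7, dispersion 1, assumed true ratios 0.6, 0.8 and 1.0.

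| | Level or line 1 | 2 | 3 |
|---|---|---|---|
| Ratio fitted directly by level | 0.592 | 0.815 | 0.992 |
| Printed vectors, reference '2' | 0.815 | 0.592 | 0.992 |
| Reordered vectors, reference '2' | 0.592 | 0.815 | 0.992 |

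This confirms the mapping; it is not evidence about the trial.

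**Reach.** Section 4.2.6 lists 16 main subgroups (the six further exploratory ones are outside the main outputs). Eight have three categories: tertiles of ferritin, TSAT, age, eGFR, creatinine and NT-proBNP/BNP, plus CKD class and LVEF class.

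- Rows per forest plot: 8 × 3 + 8 × 2 = 40; swapped: 8 × 2 = 16.
- Plots 14.2.3.1 to 14.2.3.5: 5 × 16 = 80 of 5 × 40 = 200.
- Adding the days-lost plot 14.2.3.6, which has no code of its own, if it reuses the negative binomial template: 6 × 16 = 96 of 6 × 40 = 240.

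**Cox covariates.** Section 4.6.2 has five (sex, age, hf_aetio, hf_duration, country). The subgroup template has one (sex). Omitted: 5 - 1 = 4.

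**The case against.** The strongest reply is that nothing goes wrong as printed. The three-category lines are commented out, and the active two-category vectors cannot serve a three-level factor, so a programmer has to edit the code for each such subgroup and may correct it then. The SAP allows such updates and nowhere states the 1/2/3 coding. Planned output could also expose a swap: event rates by subgroup and treatment, "lsmeans armcd armcd*subgrp / exp cl diff e" in the negative binomial code, and survival estimates by subgroup for Cox. The Cox template even holds a commented alternative that would label hazard ratios by level. On covariates, the text already governs: it repeats section 4.6.2 and says a randomisation factor used as the subgroup enters only once, which presupposes that those factors are in the model. The joint frailty code in section 4.6.1 likewise omits covariates for simplicity.

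Much of this stands, and it is why the swap is conditional and the grade low. It does not remove the point. The commented lines are the only contrasts the SAP specifies for half of the main subgroups, and uncommenting them is their evident use. A coding that made them right under reference '2' would contradict the two-category lines in the same procedure. The by-level output helps only if someone compares it with the ratios. The joint frailty code announces its omission; the Cox subgroup code does not, and it is introduced as the code to be used.

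**Conclusion.** The point holds, as a minor one. In the negative binomial and Cox templates the three-category lines exchange gr1 and gr2 under the declared reference level, which touches 8 of 16 main subgroups and 16 of 40 rows in a full forest plot. The Cox subgroup template omits four of the five covariates of the analysis it is meant to repeat.

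The swap rests on three assumptions: the lines are uncommented with reference '2' kept; levels are coded 1, 2, 3 in listed order, as the two-category lines imply; and the reference level is stored last, as those lines require. The row totals also assume that every subgroup is estimable and that the NYHA II/III subgroup is kept. The swap does not affect the NYHA plot, the two-category subgroups, the interaction p-values, the overall effects, the primary test or the Hochberg-controlled secondary tests.

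**What to change.** - For three-category runs of the negative binomial and Cox templates, set the subgroup reference to '1', as the NYHA template does. Alternatively keep reference '2' and use gr1 = `1 0 0 -1 0 0`, gr2 = `0 0 1 0 0 -1`, gr3 = `0 1 0 0 -1 0`.
- State the coding: level 1 is the first listed category, and so on.
- In the Cox subgroup template add age, hf_aetio, hf_duration and country to the model statement, and the three categorical ones to the class statement. Enter a randomisation factor only once when it is the subgroup, and replace continuous age by age tertiles for the age subgroup.

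The cost is a few lines of template code in the SAP, with no effect on data collection, sample size or the confirmatory analyses.
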